Finally, micronutrient deficiencies and excess may cause genomic damage, which could be in the same range of magnitude, or even higher, than genomic damage caused by exposure to high doses of environmental genotoxic agents such as carcinogenic agents, ultraviolet radiation and ionizing radiation (Fenech, 2010). Furthermore, since iron is not easily eliminated from the body and participates in the cell redox reactions, where ROS generate through Fenton reactions, increased iron concentrations could damage proteins, lipids and DNA permanently, causing structural and functional impairments. High plasma iron concentrations may amplify the effect of free radicals (Aksu, 2010); although cells have developed different mechanisms to reduce iron toxicity, including the regulation of iron transport through cell membranes and the production of ROS-eliminating enzymes. An imbalance of these systems caused by excess iron could increase oxidative damage susceptibility that could cause an increase in the mutation rate. These could increase the risk of developing neoplastic processes, diabetes and cardiovascular and neurological disease (Evans, 2004; Liu, 2009; Toxqui, 2010).

The effect of treatment with iron on DNA oxidation has been investigated in children with IDA, observing a significant increase of DNA strand breaks and baseline oxidative DNA damage as compared with children not receiving treatment (Aksu, 2010). However, we have not found evidence in the literature about the effect of preventive doses of iron supplementation on DNA. Therefore, we propose to compare the effectiveness of weekly and daily supplementation for the prevention of anemia in infants less than six months of life and to analyze their impact on genomic stability.

Objectives

General: To compare the effectiveness of weekly and daily iron supplementation for the prevention of anemia in infants.

Specific: To compare:

- To compare the effectiveness of weekly, daily and no iron supplementation at six months of age in EBF infants.
- To compare the effectiveness of weekly and daily iron supplementation in six-month-old infants receiving MF.
- To compare the incidence of adverse effects for weekly and daily iron supplementation at six months of age.
- To compare the adherence to treatment of weekly and daily iron supplementation at six months of age.
- To compare the concentration of oxidative stress biomarkers for both types of iron supplementation.

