- To compare the genomic damage in both types of iron supplementation.

Study hypothesis

Weekly ferrous sulfate supplementation will be more effective in the prevention of IDA in infants than daily supplementation due to a higher adherence and a lower incidence of adverse effects. Weekly iron supplementation will cause less genomic instability as compared with daily iron supplementation.

Study design

Randomized controlled clinical trial.

Study sample

Eligibility

Infants performing monthly health controls at the Pediatric Health Observatory of IDIP, La Plata Children's Hospital, from birth to six months of age will be included in the study.

Inclusion, exclusion and elimination criteria

Inclusion criteria: Three-month-old clinically healthy breastfeeding infants with birth age > 37 weeks, birth weight between 2500 and 4000 g, a normal fetal and neonatal history, that attend IDIP's Health Observatory and whose parents/guardians express the will to participate in the study and sign a written informed consent form.

Exclusion criteria: Anemic and/or iron deficient infants or with chronic diseases or acute infections or under antibiotic/vitamin treatment within 15 days prior to the study.

Elimination criteria: infants with severe intolerance to iron preventive supplementation, who will receive the alternative preventive treatment with ferrous fumarate or iron polymaltose complex).

Unit of analysis: Three to six month-old infants.

Sample size and selection

According to ENNyS, the prevalence of anemia in 6-9 months old infants is 50.8%. Our controlled interventions would reduce such prevalence to 30%. Sample size was estimated with 0.95 significance level and 0.80 power, resulting in 174 infants (n= 87 for each supplementation group). This number was adjusted considering a 15% dropout, thus enrolling 204 infants.

Methods

Operational definition of variables

Main variables

-Anemia is defined as the “decrease in the total amount of blood cells or a blood hemoglobin (Hb) concentration more than 2 standard deviations below the mean of an age- and sex-matched reference range”. We will define the presence of anemia when Hb < 9.5 g/dL at 3 months of age and Hb < 11.0 g/dL at six months of age (CDC, 2007).

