-Iron deficiency is defined as insufficient iron in the body. It will be considered when blood ferritin <12 ng/ml (WHO 2001). Since ferritin is an acute phase reactant, we will measure C-reactive protein (CRP) to assess an eventual inflammatory state. When CRP is ≥ 5 mg/L, ID will be defined by a blood ferritin <30 ng/ml. The soluble transferrin receptor (sTfR) which is not influenced by inflammation will also be used (cut-off value, sTfR 8.3 mg/L) (Grant 2012).

Secondary variables

-Adverse effects: presence (or absence) and frequency of one or more of the following effects during ferrous sulfate supplementation (rejection, constipation, vomiting, diarrhea, abdominal pain).

-Adherence to treatment: is the rate of adherence to medication intake, dietary plan or lifestyle changes according to recommendations agreed on with healthcare professionals (OMS, 2003).

Adherence will be measured with the formula:

$$\frac{(\text{ml SO}_4\text{Fe received} - \text{ml SO}_4\text{Fe remaining})}{\text{days between the medication vial delivery and its return}} \times 100$$

where ml SO₄Fe received is the volume of ferrous sulfate delivered in a vial, sufficient to cover the prescription until the infants' next control (1 month), and ml SO₄Fe remaining is the residual volume in the vial at the moment of the health control.

We will consider low adherence the consumption of less than 50% of the amount of medication

prescribed for the study period, and less than 50% of intakes prescribed for the study period.

We will consider high adherence consumption of more than 80% of the amount prescribed and more than 80% of the intakes prescribed.

All combinations not covered by low and high adherence will be considered as moderate adherence.

-Genomic instability: Chromosome, DNA and cell damage caused by certain agents. We will evaluate oxidative stress and genomic damage at cytomolecular level and at DNA base level.

- Oxidative stress: imbalance between reactive oxygen species (ROS) production and accumulation and the counteracting enzymatic/non-enzymatic antioxidant mechanisms. We will measure catalase and superoxide-dismutase enzymatic activity and evaluate cell damage by lipid peroxidation through thiobarbituric acid-reactive substances (TBARS) assessment.

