- Genomic damage: DNA damage assessed by cytomolecular techniques using the Comet assay (damage index assessment in 200 cells, quantifying damage by Tail moment and Olive Tail moment). The frequency of oxidized DNA bases will be determined by competitive 8-oxo-dG Elisa.

Other variables:

- Sex, weeks of gestation, umbilical cord clamping.

- Infant nutritional condition will be assessed by anthropometry (weight, height, head circumference) at three and six months.

- Sociodemographic data of infants and relatives, including place of residence, unsatisfied basic needs, maternal education.

- Maternal nutritional condition will be evaluated with anthropometry and iron status.

- Environmental exposure to genotoxic agents (antibiotics, radiation (X-rays) and chemical substances like pesticides, solvents and industrial waste) will be assessed by questionnaire.

Data collection

-Patient enrolment

During health control visits to IDIP Health Observatory on the first and second month of life, parents and tutors will be invited to participate in the study; the study's protocol, its aims and benefits will be explained in a plain language. They will be asked to sign a written informed consent form in case they accept their children be incorporated to the study. Infants meeting the inclusion criteria with exclusively breastfeeding (EBF) will be randomly divided into three groups: weekly, daily and no supplementation. Those with mixed feeding (breastfeeding and formula; MF) will be randomly divided into two groups: weekly and daily supplementation.

- Intervention

Weekly supplementation (EBF or MF): infants will receive a weekly dose of ferrous sulfate (4mg/kg/week).

Daily supplementation (EBF or MF): infants will receive a daily dose of ferrous sulfate (1 mg/kg/day).

Without intervention (only EBF): infants will receive no supplementation, following the current SAP guidelines. Ferrous sulfate will be supplied by pediatricians.

- Randomization

Randomization will be performed by computer-generated random sequences of numbers in blocks of variable length. Randomization will be stratified by type of intake (EBF or MF).

Treatment assignments will be placed in sequentially numbered, opaque and sealed envelopes which will be consecutively put in a box and later removed one at a time. The person in charge of the random allocation process will not take part in the enrollment process.

- Blinding

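### The adherence formula yields 100 × ml used per day, not a percentage of the amount prescribed, and it scores equally adherent weekly and daily infants differently

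*Protocol*

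**What the plan says.** Protocol, Operational definition of variables, Secondary variables: "Adherence will be measured with the formula" is followed by a fraction. Its numerator is the volume of ferrous sulfate received minus the volume remaining. Its denominator is "days between the medication vial delivery and its return", and the result is multiplied by 100. The explanatory list under the formula defines only the received and remaining volumes.

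The same section then sets the categories:
- Low, by volume: "We will consider low adherence the consumption of less than 50% of the amount of medication" due. A second condition, on the number of doses taken, must also be met: "less than 50% of intakes prescribed for the study period".
- High: "We will consider high adherence consumption of more than 80% of the amount prescribed and more than 80% of the intakes prescribed".
- Moderate: every other combination.

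The Intervention section gives 4 mg/kg/week in the weekly arm and 1 mg/kg/day in the daily arm. Sample collection. Surveys sets 12 weeks of supplementation. Under Intervention progress monitoring, leftover dropper volume is checked at each monthly control, and parents keep a separate record of intakes.

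A specific objective is "To compare the adherence to treatment of weekly and daily iron supplementation at six months of age". The Study hypothesis expects weekly dosing to do better "due to a higher adherence and a lower incidence of adverse effects". The Data analysis section plans a relative risk, with 95% CI, of low adherence for weekly against daily dosing.

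**The concern.** The formula has units of ml per day, scaled by 100. The categories need a percentage of what was prescribed. The term that would link the two, the prescribed volume, is absent from both the formula and its list of definitions.

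The omission does not cancel between the arms. The weekly arm is prescribed less iron per calendar day, so it scores lower on the formula at the same true adherence. Adherence is compared between exactly these two arms, and the result is part of the trial's explanation of why weekly dosing should work. An analyst who takes the printed score as the amount percentage could classify infants wrongly, and differently by arm.

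**Working it through.** **Inputs from the protocol.** Weekly dose 4 mg/kg/week and daily dose 1 mg/kg/day (Intervention); 12 weeks, which is 84 days (Sample collection. Surveys); cut-offs of 50% and 80% (Secondary variables). The protocol prints no adherence value to reproduce.

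**Not given in the protocol.** Product concentration C (mg/ml) and body weight W (kg). Where they are needed I assume C from 5 to 50 mg/ml and W from 5.5 to 7.5 kg.

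**1. The formula as written.** Let a be the true fraction of the prescribed amount taken.
- Daily arm: score = 100 × a × W/C.
- Weekly arm: score = 100 × a × (4/7) × W/C.

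A fully adherent infant (a = 1) scores 100 only if the prescription is exactly 1 ml per calendar day. That needs C = W in the daily arm and C = 4W/7 in the weekly arm, so one product cannot satisfy both at the same weight.

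**2. Ratio between arms.** Full adherence over 12 weeks uses 84 × 1 = 84 mg/kg daily and 12 × 4 = 48 mg/kg weekly. The ratio is 48/84 = 0.571, whatever C and W are, provided they and the interval are the same in both arms.

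**3. Where the 50 cut-off falls.** A score below 50 means a < 0.5 × C/W in the daily arm and a < 0.875 × C/W in the weekly arm. The ratio is 0.875/0.5 = 84/48 = 1.75.
- C/W = 1: the cut-offs are a true 50% (daily) and 87.5% (weekly).
- C/W = 4/7: they are 28.6% (daily) and 50% (weekly).

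**4. Scores at full adherence over the assumed range.**

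| C (mg/ml) | W (kg) | Daily | Weekly |
|---|---|---|---|
| 5 | 5.5 | 110.0 | 62.9 |
| 5 | 7.5 | 150.0 | 85.7 |
| 10 | 5.5 | 55.0 | 31.4 |
| 10 | 7.5 | 75.0 | 42.9 |
| 25 | 5.5 | 22.0 | 12.6 |
| 25 | 7.5 | 30.0 | 17.1 |
| 50 | 5.5 | 11.0 | 6.3 |
| 50 | 7.5 | 15.0 | 8.6 |

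From 10 mg/ml upward, no fully adherent infant exceeds 80 in either arm, and no fully adherent weekly infant reaches 50.

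**5. Effect on the low category.** Low requires an amount score below 50 and intakes below 50%. The weekly amount cut-off is always the higher one. With the same C, W and joint distribution of amount and intakes in both arms, the weekly arm can therefore show only as many low infants or more. Two illustrations:
- Amount and intakes both truly 45%, C = 5, W = 6.5: daily score 0.45 × 130.0 = 58.5 (not low); weekly score 58.5 × 4/7 = 33.4 (low). Both are truly low. The arms split in this way only for C/W above 0.45/0.875 = 0.51 and up to 0.45/0.5 = 0.90.
- Amount truly 60%, intakes 45%, C/W = 1: daily score 60 (not low); weekly score 60 × 4/7 = 34.3 (low). Both are truly moderate.

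**6. After correction.** The prescribed volume per calendar day is W/C (daily) or (4/7) × W/C (weekly). Dividing ml used by the volume prescribed for the interval gives 100 × a in both arms. True intakes of 100%, 80% and 50% return 100, 80 and 50, whatever C and W are.

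**The case against.** The strongest reply is that the analyzed outcome is defined correctly in words. Harm arises only if someone reads the printed score as the amount percentage, and even then the intake criterion limits it. If amount and intakes agree and C/W is 1 or more, both amount cut-offs are at least 50%, so the intake criterion decides and low is classified correctly in both arms. If C/W is 2 or more, every infant taking less than the full prescribed amount meets the amount criterion, so intakes alone decide. With C from 10 to 50 mg/ml and W from 5.5 to 7.5 kg, C/W is never below 10/7.5 = 1.33. In that range it is mainly the high category that fails, and no between-arm analysis of high adherence is planned.

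All of this stands, and it means the factor of 1.75 is not a measure of bias in the relative risk. It does not rescue the formula. The protocol says adherence will be measured with it, and it is the only calculation given for the dropper volumes. C and W are not stated, so the harmless case cannot be assumed. Amount and intakes come from different sources and may disagree.

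A second point also stands: 4/7 is exact only over whole weeks. Over a 30-day interval the daily arm is due 30 mg/kg and the weekly arm 16 or 20 mg/kg (4 or 5 doses), giving ratios of 16/30 = 0.53 or 20/30 = 0.67. The arms still differ.

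A term lost in text conversion is unlikely, because the list under the formula defines no prescribed volume either.

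**Conclusion.** The concern holds. As printed, the formula gives 100 × ml per day and cannot be read against the 50% and 80% cut-offs beside it. At equal weight, concentration and whole-week interval, the weekly score is 0.571 of the daily score for the same true adherence, which follows from the stated doses alone. If the score is used as the amount percentage, the 50 cut-off falls at a true intake 1.75 times higher in the weekly arm.

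At equal true adherence, any resulting difference in the low category runs against the weekly arm, and so against the trial's hypothesis. Its size in the relative risk cannot be derived from the protocol and may be zero. The verbal definitions are right, and the anemia relative risk does not depend on the formula. This is a wrong rule for a secondary objective and should be corrected before adherence is scored.

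**What to change.** Replace the formula with: amount adherence (%) = total ml used over the study period (delivered minus remaining) ÷ total ml prescribed for the same period in the infant's arm × 100. Take ml prescribed as the ml per dose times the number of doses due in the period, which also deals with intervals that are not whole weeks. Do not use ml delivered as the divisor, because the vial may hold more than was prescribed.

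Apply the existing 50% and 80% amount cut-offs to this percentage. Keep the separate intake criterion and the requirement that both be met.

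The cost is one formula and, if it is not already recorded, one field (prescribed ml per dose) in the intervention registry that the Work plan already calls for. Dropper volumes and intake records are already collected at each monthly control. No dose, visit or sample size changes.

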Pediatricians in charge of supplementation will know the assigned intervention only when the envelopes are open. Professionals in charge of performing laboratory tests will not know intervention assignments.

-Sample collection. Surveys

Before supplementation, 3-ml blood samples from infants will be drawn to assess anemia, ID, and genomic stability. All non-anemic/iron deficient infants will be recruited and will be supplemented

according to the group assigned during 12 weeks (three months). At the end of this period (six months of age), blood samples will be drawn again to measure the study variables. Infant and family sociodemographic data will be surveyed at the first visit (three months of age). Anthropometric measurements will be taken at three and six months. Nutritional assessment of the mothers will be performed at the beginning and at the end of the study, measuring weight and height and drawing blood samples for anemia and ID assessment.

- Intervention progress monitoring

Pediatricians will prescribe iron doses and manner of administration. Parents and/or tutors will receive one or more droppers with ferrous sulfate sufficient to complete one-month supplementation, considering that all infants will perform monthly health controls. The Telegram program “LactaPlusIDIPBOT”, designed at IDIP, will be used to send reminders for iron supplement intake. They will be also contacted weekly (Facebook messenger, Whatsapp, Telegram). To monitor adherence, we will use a daily/weekly consumption record form that will be completed by parents/tutors and delivered at each health control. To determine consumption, we will control de excess volume in droppers during each monthly control.

- Record of adverse effects

Parents and/or tutors will receive a form to register adverse effects which will be presented at each monthly control. They will register intake rejection, constipation, vomiting, diarrhea, and abdominal pain. Infants with intolerance to iron supplementation will be excluded from the study but will continue on an alternative treatment (1 mg/kg/day fumarate or iron polymaltose complex).

- Laboratory tests

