Blood samples (3 ml) from infants will be drawn at IDIP’s laboratory by venipuncture and divided into two vials: 1) an EDTA tube containing 1 ml blood for complete blood count, and 2) lyophilized lithium heparin tube that will be centrifuged to obtain plasma for the assessment of ferritin, CPR, sTfR, 8-oxodG and TBARS, and erythrocytes for the assessment of CAT and SOD determinations and for the Comet assay. The following methods will be used:

Hemoglobin: Modified Drabkin method (ABX Pentra DX 120 Horiba).

Ferritin and sTfR: enzymatic immunoassay using a chemiluminescence substrate (Access-Beckman Coulter, Fullerton, US).

C-reactive protein: turbidimetry (Autoanalyzer BT 3000 Plus Wiener).

All these tests will be performed at the Children’s Hospital Central Laboratory.

Cytomolecular genomic stability: alkaline version of the Comet assay (electrophoresis of a cell sample previously embedded in agarose, being migration proportional to the damage present (Sinh et al., 1988, Padula 2016).

ROS-mediated DNA damage: ELISA to quantify 8-oxodG, the most frequently oxidized nucleotide (Rossner et al 2006; Rossner & Sram 2012).

These tests will be performed at IGEVET.

CAT activity: spectrophotometry using Aebi’s method.

SOD activity: commercial kit (Ransod; RandoxLabs).

TBARS: spectrophotometry according to Okhawa.

These tests will be performed at IDIP and IGEVET.

Iron nutritional status (hemoglobin and ferritin) of mothers: blood samples taken at three and six months after delivery.

Data analysis

The effectiveness of the interventions will be evaluated at six months of age by comparing the incidence of anemia in both study groups as a relative risk (RR) and its corresponding 95% confidence interval (95% CI). For the EBF group, no supplementation will be the reference category, whilst for the MF group, the reference category will be daily iron supplementation.

Intention-to-treat analysis will be used to account for the possible changes in type of feeding and/or intervention arms. However, per-protocol analysis will be also performed and compared with intention-to-treat analysis in order to determine the result robustness.

Losses to follow-up will be censored since analyses will be performed in closed cohorts because we will not be able to estimate incidence density (we will only collect data on anemia and ID at three and six months).

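### Infants are excluded from the study after randomisation for intolerance to the assigned iron, which conflicts with the stated intention-to-treat analysis

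*Protocol*

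**What the plan says.** Two places in the protocol remove infants for intolerance to iron.

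- Inclusion, exclusion and elimination criteria: "Elimination criteria: infants with severe intolerance to iron preventive supplementation". This stands apart from the exclusion criteria that apply before entry.
- Record of adverse effects: "Infants with intolerance to iron supplementation will be excluded from the study but will continue on an alternative treatment". Here the intolerance need not be severe.

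The Data analysis section takes a different line on who is analysed: "Intention-to-treat analysis will be used to account for the possible changes in type of feeding and/or intervention arms". It adds that "per-protocol analysis will be also performed and compared with intention-to-treat analysis in order to determine the result robustness". Losses to follow-up are to be censored, and the reason given is that "we will only collect data on anemia and ID at three and six months".

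Two further statements bear on the point. The study hypothesis expects weekly iron to do better than daily iron "due to a higher adherence and a lower incidence of adverse effects". The Intervention section gives one of the three exclusively breastfed (EBF) groups no supplement, and Data analysis makes that group the EBF reference category.

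**The concern.** An infant who cannot tolerate ferrous sulfate and moves to another iron product has changed treatment after randomisation. Intention-to-treat analysis exists to keep such infants in their allocated arm. A rule that takes them out of the study defeats it.

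The removal also depends on the arm. The EBF reference group cannot lose anyone this way, and daily iron should lose more infants than weekly iron if the hypothesis is right. Lower intolerance is part of the reason offered for weekly iron being more effective, so removing intolerant infants removes part of the contrast under study.

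At stake is the main result, the relative risk (RR) of anemia at six months. It could compare groups that are no longer as randomised. The planned comparison of intention-to-treat with per-protocol results would also be a weaker check, because both sets may lack the same infants. They would still differ in other ways, such as adherence and changes of feeding or arm.

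**Working it through.** **Reading the passages together**

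1. Recruited infants are supplemented according to the assigned group, so intolerance arises after allocation.
2. The text removes intolerant infants from the study, not merely from the product, and the eligibility section calls this elimination.
3. No visible passage keeps their follow-up or their six-month sample. That the sample is lost is therefore an inference. It is not stated, and the study flowchart is not shown.
4. Anemia is measured only at three and six months. With one measurement after baseline, censoring a loss amounts to leaving the infant out of the RR.

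**The plan's own figures**

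The sample size uses anemia risks of 50.8% and 30%, with "n= 87 for each supplementation group". The usual two-sided 5% test with 80% power and pooled variance, without continuity correction, gives 87 per group and 174 in total, which matches. For 15% dropout, 174/0.85 = 204.7, against the protocol's "thus enrolling 204 infants". These figures are not in dispute and serve below only as planning values.

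**Illustration of the possible bias**

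The protocol gives neither an intolerance rate nor an anemia risk in intolerant infants. Both are assumed here.

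Observed risk in an arm = (p − x·r)/(1 − x), where

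- p = 0.30, the planned risk under intervention, taken as true in both the daily and the weekly arm (true RR 1.00);
- x = share of the arm excluded (assumed);
- r = anemia risk in those excluded, 0.2 to 0.6 (assumed).

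Example: daily arm, x = 0.10, r = 0.6: (0.30 − 0.06)/0.90 = 0.267. With no weekly exclusions, RR = 0.300/0.267 = 1.125.

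The EBF comparison of daily iron with no supplementation uses 0.508 for the reference group, which loses nobody, so the true RR is 0.300/0.508 = 0.591.

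| r | Daily risk, x = 10% | Weekly/daily RR, 10% and 0% excluded | Weekly/daily RR, 10% and 5% | Weekly/daily RR, 5% and 0% | EBF daily/none RR, 10% of daily |
|---|---|---|---|---|---|
| 0.2 | 0.311 | 0.964 | 0.981 | 0.983 | 0.612 |
| 0.3 | 0.300 | 1.000 | 1.000 | 1.000 | 0.591 |
| 0.4 | 0.289 | 1.038 | 1.020 | 1.018 | 0.569 |
| 0.5 | 0.278 | 1.080 | 1.042 | 1.036 | 0.547 |
| 0.6 | 0.267 | 1.125 | 1.066 | 1.056 | 0.525 |

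A lower exclusion share gives less. With 2% of daily and no weekly infants excluded, RR = 0.300/[(0.30 − 0.02r)/0.98], which is 0.99 at r = 0.2 and 1.02 at r = 0.6.

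**Scale against sampling error**

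With 87 per arm and 30% risk, SE(log RR) = √(2 × 0.70/(87 × 0.30)) = 0.232. The 95% confidence interval around 1.00 is exp(±1.96 × 0.232), about 0.64 to 1.57. If the 174 infants were instead spread evenly over the five feeding-by-treatment groups (an assumption; 174/5 is about 35 each), it would be about 0.49 to 2.05. Each weekly/daily shift in the table is smaller than either interval.

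**The case against.** The strongest reply is that the loss of data is inferred. Data analysis says intention-to-treat will cover changes of intervention arm, and a switch to another iron product could count as one. All infants are expected at monthly controls, so those excluded may still be reachable at six months. On that reading, exclusion means only stopping the study product. This is possible, but it goes against the wording: the text says from the study, the eligibility section says elimination, and nothing provides for continued sampling. Even if the milder meaning was intended, staff would act on what is written.

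Second, the protocol already censors losses and allows 15% dropout, and these infants may fall within that allowance. That may protect the numbers, but it does not undo selection by arm.

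Third, the exclusion rate may be small, particularly if only severe intolerance counts. This stands: at 2% the shift is about 0.02 or less.

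Fourth, if intolerant infants have above-average anemia risk, the weekly/daily RR moves above 1, against the protocol's hypothesis, so the bias would be conservative there. This also stands, but only under that assumption. The same assumption flatters daily iron against no supplementation in EBF infants, and below-average risk reverses both effects. Intolerant infants continue on another iron product, so their risk cannot be guessed from the protocol.

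**Conclusion.** The concern holds: the rule is wrong as written. Exclusion from the study for intolerance contradicts the intention-to-treat analysis, and the two statements of the trigger disagree. That much is certain from the text. The loss of the six-month hemoglobin is the natural reading but remains an inference.

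The size and sign of any bias are unknown. Under the assumed values, a true weekly/daily RR of 1.00 would read between 0.96 and 1.13, and a true EBF daily/none RR of 0.59 between 0.61 and 0.52. There is no bias if excluded infants have average risk. These figures show what is possible, not what is likely, and the weekly/daily shifts are smaller than sampling error. Unlike sampling error, however, such a shift is not reflected in the confidence interval and would not shrink with more infants. The protocol should be corrected because this is a data-collection rule: a hemoglobin that was never measured cannot be restored by an analysis plan.

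**What to change.** In the record of adverse effects, replace exclusion from the study with a statement that infants who stop the assigned ferrous sulfate for intolerance stay in follow-up, have the planned six-month sample, and are analysed in the arm to which they were randomised. In the eligibility section, let the elimination criterion define only who leaves the per-protocol set, and leave its provisions on care as they are. Reconcile severe intolerance with intolerance so that one trigger applies throughout; which one is for the investigators to decide.

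The cost is protocol wording, plus the already scheduled 3-ml venipuncture for infants who would otherwise have left, subject to continued consent. For a rough count, suppose the 204 enrolled were split as 102 daily and 102 weekly. This is a simplification, since it leaves none for the unsupplemented EBF group. Excluding 10% of daily infants (10.2) and 0% to 5% of weekly infants (0 to 5.1) would mean about 10 to 15 samples. Clinical care does not change.
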